## Schema of Study Visits and Corresponding Study Week and Day

Part 1	Part 2													Part 3							
	•							Ope	en-lab	el								]	Double-	Blind	
÷		q																		ntrolled, on Phase ks)	÷
											Vi	isit N	lumbe	r							
1	2	(T)	3	(T)	4		(T)		5		(T)		6		(T)		7	8	9	10	11
										Beg	ginni	ng of	f Study	Wee	k						
1	2	3	4	5	6	7	8	9	10	1	1 2	1 3	14	15	16	17	18	19	20	21	
										Cor	resp	ondi	ng Stu	dy Da	ıy						
1	8	15	22	29	36				64				92				120	127	134	141	148

Approximately 300 subjects will be enrolled to ensure that at least 240 subjects are randomized in Part 3;  e. Subjects will be screened for eligibility within 14 days of the initial visit by medical history, recent and concomitant medication use, physical and neurological examination, 12-lead ECG, clinical laboratory testing, and assigned a subject number. Upon successful screening and provision of informed consent, eligible subjects will be enrolled in the study (Visit 1). Once on study, subjects will be seen in the clinic at the end of the 7-day run-in (Visit 2), at which point they will be converted to described in Section 4.3.1). They will be seen in the clinic every 2 weeks during
; subjects are to be contacted by telephone during the intervening weeks
). As described in Section 4.3.1, dose adjustments will be allowed during this 4-week phase; dose adjustments may only be made at a clinic visit, including at an unscheduled meeting if needed.
At the beginning of (Visit 7), subjects who have remained on a fixed dose of without further need for adjustment in medication, will be
randomly assigned to either remain on In subjects
All subjects will be seen in the clinic every week (see Table 1) or sooner, if required.
every week (see Table 1) of sooner, it required.
study visit is Subjects will be encouraged to continue study participation to the end of the trial. In subjects
Subjects will be instructed to take study drug at the same time of day, 30 minutes following the evening meal. Throughout the study, clinic visits should be timed to occur at approximately the same time of day relative to dosing. Clinic conditions, e.g. , ambient temperature and lighting, should be kept as consistent as possible. Similarly, concomitant physiotherapy should also not change during the course of the study.
Subjects will be evaluated for efficacy as briefly described below. The efficacy instruments and assessments are further described in Section 8.1.
•

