## 3.1.3 Exoploratory Objectives

#### 3.2 Study Design

The study is a multicenter, out-patient trial in subjects with spasticity due to MS (Multiple Sclerosis). The study will be performed in three parts: a 1-week open-label phase (Part 1)

week open-label phase (Part 2)

a 16-

and a 4-week, double-blind, placebo-controlled, randomized withdrawal phase (Part 3). Subjects will be informed that at some time during the study, they may receive placebo, however, they will not be informed at which visit this will commence. An overview scheme of the study and the schedule of events are presented in Section 3.2.3.

Approximately 300 subjects will be enrolled to ensure that at least 240 subjects are randomized in Part 3. Subjects will be screened for eligibility within 14 days of the initial visit by medical history, recent and concomitant medication use, physical and neurological examination, 12-lead ECG, clinical laboratory testing, and assigned a subject number. Following provision of informed consent and successful screening, eligible

Version 9.0

subjects will be enrolled in the study (Vis	it 1). Once on study, subjects will be seen in the
clinic at the end of the 7-day	(Visit 2), at which point they will be
converted to	. They will be seen in the clinic every 2 weeks
	_

subjects are to remain on a fixed dose for an additional 12 weeks;

At the beginning of Week 18 (Visit 7), subjects who have remained on a fixed dose of for 12 to 16 weeks, without further need for adjustment in medication, will be randomly assigned to either remain on in the same dose or placebo for an additional 4 weeks.

The final scheduled study visit is Visit 11,

Subjects will be evaluated for efficacy as briefly described below. The efficacy instruments and assessments are further described in Section 6.2.

Right and left hip flexion and abduction, knee flexion and extension, and ankle dorsiflexion and plantar flexion will be assessed using the modified

Ashworth Scale, 6-point version (inclusive of 1+), rated from 0 to 4, for a total of 12 movements being evaluated. This same individual will query the subject for any changes in physiotherapy regimen. The modified Ashworth Scale assessment is further discussed in Section 6.2.1.

• Clinician Global Impression of Change (CGIC) will be assessed by the Treating Physician,

The Subject Global Impression of Severity (SGIS) will be assessed at Visits 4, 7, 8, 9, 10, and 11.

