### 6.1.8 Exposure and Compliance

Exposure data at each visit starting with Visit 1 will be summarized for the Safety Population for Parts 1 and 2, and for Part 3, separately. Specifically, the numbers of subjects for each dose level will be summarized with counts and percentages, and descriptive summaries (mean, 95% confidence interval, median, mode, and standard deviation) of dose at each visit will be provided. The number of tablets of exposure will be calculated for each visit and will also be summarized, where the exposure is calculated as (number of tablets dispensed – number of tablets returned). Exposure duration for each visit will also be summaried, where duration is calculated as ((last dose date – first dose date) + 1). For Safety Population Part 3, summaries will be included of down-titration exposure in the placebo randomized group.

Study medication will be dispensed by the site personnel with the amount dispensed and the amount returned documented in the eCRF. Treatment compliance will be calculated using the number of capsules dispensed minus the number of capsules returned, divided by the number of capsules intended to be taken. Average compliance will be summarized descriptively by visit, and for the study overall. A further categorical summary of compliance will be provided by visit, and for the study overall, using the following categories: <75%,  $\ge75\%$  to  $\le125\%$ , and >125%.

Individual subject listings of dosing will be prepared, based on dispense dates and subject diary data. A separate listing of drug accountability will be prepared.

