#### • Missing AE Stop Dates

If the stop date is completely missing and the event is not ongoing (i.e., an outcome is indicated), the stop day will not be estimated.

If only the day of resolution is unknown, the day will be assumed to the last of the month (e.g. ??-JAN-2011 will be treated as 31-JAN-2011)

If the stop date is completely missing and the event is ongoing, the event will be noted as "Ongoing" in the stop date column in the AE listings.

The incidence of TEAEs and serious adverse events (SAEs) will be summarized

An overall summary of TEAEs will include:

- o Incidence of subjects with one or more TEAE
- o Incidence of TEAEs by highest relationship
- o Incidence of TEAEs by highest severity
- o Incidence of TEAEs by action taken
- o Incidence of TEAEs by outcome
- o Incidence of treatment-emergent SAEs

The incidence of TEAEs will be presented by system organ classification and preferred terms, by highest relationship, by treatment-related status (possibly, probably, certainly), by highest severity, by descending order of frequency of preferred terms, by dose at earliest onset for all possible dose groups, and by discontinuation status.

In addition, separate summaries of TEAEs will be prepared with subjects categorized by sex, age (below 65 years of age and 65 years of age and older), race, and renal impairment category (see Section 6.1.2).

The effects of concomitant medications and/or medical conditions present at screening will also be explored. Should any medications be used by or conditions be present in 20% or more of the subjects overall, subjects will be categorized accordingly and the incidence of TEAEs in each part summarized. Additional drugs or diagnoses of interest may be identified during the blinded data review.

The incidence of treatment-emergent serious adverse events (SAEs) will be presented by system organ classification and preferred terms, by treatment-related status (possibly, probably, certainly), and for those that are fatal.

Adverse events will be listed for all subjects, including verbatim and coded terms.

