	Incidence of Treatment-Emergent Adverse Events by Descending Order of Frequency
Table 14.3.1.1.3	of Preferred Terms in Part 2 (Safety Population)
Table 14.3.1.1.4	Incidence of Treatment-Emergent Adverse Events by Maximum Severity in Part 2 (Safety Population)
14010 14.5.1.1.4	Incidence of Treatment-Emergent Adverse Events by Highest Relationship in Part 2
Table 14.3.1.1.5	(Safety Population)
	Incidence of Treatment-Related Treatment-Emergent Adverse Events by Highest
Table 14.3.1.1.6	Relationship in Part 2 (Safety Population)
Table 14.3.1.1.7	Incidence of Treatment-Emergent Adverse Events Leading to Discontinuation in Part 2 (Safety Population)
14016 14.5.1.1./	Incidence of Treatment-Emergent Adverse Events by Gender in Part 2 (Safety
Table 14.3.1.1.8	Population)
Table 14.3.1.1.9	Incidence of Treatment-Emergent Adverse Events by Age Group in Part 2 (Safety
	Population)
Table 14.3.1.1.10	Incidence of Treatment-Emergent Adverse Events by Race in Part 2 (Safety
Table 14.3.1.1.11	Population) Incidence of Treatment-Emergent Adverse Events by Concomitant Medications in at
14010 14.5.1.1111	Least 20% of Subjects in Part 2 (Safety Population)
Table 14.3.1.1.12	Incidence of Treatment-Emergent Adverse Events by Medical Conditions Present in
	at Least 20% of Subjects at Screening in Part 2 (Safety Population)
Table 14.3.1.1.13	Incidence of Treatment-Emergent Adverse Events by Renal Function in Part 2 (Safety
	Population) Incidence of Treatment-Emergent Adverse Events by Dose at Earliest Onset in Part 2
Table 14.3.1.1.14	(Safety Population)
Table 14.3.1.2.1	Overview of Adverse Events by Treatment Group in Part 3 (Safety Population)
14010 1 1.0.1.2.1	Incidence of Treatment-Emergent Adverse Events by Treatment Group in Part 3
Table 14.3.1.2.2	(Safety Population)
	Incidence of Treatment-Emergent Adverse Events by Descending Order of Frequency
Table 14.3.1.2.3	of Preferred Terms by Treatment Group in Part 3 (Safety Population)
	Incidence of Treatment-Emergent Adverse Events by Maximum Severity by
Table 14.3.1.2.4	Treatment Group in Part 3 (Safety Population)

	Incidence of Treatment-Emergent Adverse Events by Highest Relationship by	
Table 14.3.1.2.5	Treatment Group in Part 3 (Safety Population)	
Table 14.3.1.2.6	Incidence of Treatment-Related Treatment-Emergent Adverse Events by Highest Relationship by Treatment Group in Part 3 (Safety Population)	

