Table 14.3.1.2.7	Incidence of Treatment-Emergent Adverse Events Leading to Discontinuation by Treatment Group in Part 3 (Safety Population)	
Table 14.3.1.2.8	Incidence of Treatment-Emergent Adverse Events by Gender by Treatment Group in Part 3 (Safety Population)	
Table 14.3.1.2.9	Incidence of Treatment-Emergent Adverse Events by Age Group by Treatment Group in Part 3 (Safety Population)	
Table 14.3.1.2.10	Incidence of Treatment-Emergent Adverse Events by Race by Treatment Group in Part 3 (Safety Population)	
Table 14.3.1.2.11	Incidence of Treatment-Emergent Adverse Events by Concomitant Medications in at Least 20% of Subjects by Treatment Group in Part 3 (Safety Population)	
Table 14.3.1.2.12	Incidence of Treatment-Emergent Adverse Events by Medical Conditions Present in at Least 20% of Subjects at Screening by Treatment Group in Part 3 (Safety Population)	
Table 14.3.1.2.13	Incidence of Treatment-Emergent Adverse Events by Renal function by Treatment Group in Part 3 (Safety Population)	
Table 14.3.1.2.14	Incidence of Treatment-Emergent Adverse Events by Dose at Earliest Onset by Treatment Group in Part 3 (Safety Population)	
Table 14.3.2.1.1	Incidence of Treatment-Emergent Serious Adverse Events in Part 2 (Safety Population)	
Table 14.3.2.1.2	Incidence of Treatment-Related Treatment-Emergent Serious Adverse Events by Highest Relationship in Part 2 (Safety Population)	
Table 14.3.2.1.3	Incidence of Fatal Treatment-Emergent Serious Adverse Events in Part 2 (Safety Population)	
Table 14.3.2.2.1	Incidence of Treatment Emergent Serious Adverse Events by Treatment Group in Part 3 (Safety Population)	
Table 14.3.2.2.2	Incidence of Treatment-Related Treatment-Emergent Serious Adverse Events by Highest Relationship in Part 3 (Safety Population)	
Table 14.3.2.2.3	Incidence of Fatal Treatment-Emergent Serious Adverse Events in Part 3 (Safety Population)	
Table 14.3.4.1.1	Vital Signs in Part 2 (Safety Population)	
Table 14.3.4.1.2	Vital Signs in Part 3 (Safety Population)	
Table 14.3.4.1.3	Potentially Clinically Significant Vital Signs in Part 2 (Safety Population)	
Table 14.3.4.1.4	Potentially Clinically Significant Vital Signs in Part 3 (Safety Population)	
Table 14.3.4.2.1	Hematology Laboratory Assessments (Safety Population)	
Table 14.3.4.2.2	Hematology Laboratory Shift Table (Safety Population)	
Table 14.3.4.2.3	Number and Percentage of Subjects with a Possibly Clinically Significant (PCS) Hematology Results – Safety Population	

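### Part 2 TEAE incidence by dose at earliest onset takes no account of time at each dose, so the table can mimic or mask a dose effect

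*SAP*

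**What the plan says.** SAP 6.3.1 lists several TEAE incidence displays, one of them "by dose at earliest onset for all possible dose groups". SAP 9.1 turns this into Table 14.3.1.1.14, "Incidence of Treatment-Emergent Adverse Events by Dose at Earliest Onset in Part 2", and into Table 14.3.1.2.14, the same display by treatment group for Part 3.

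Dose can move early in Part 2 and is then held. Protocol 4.1 allows adjustment during a 4-week conversion phase, and "dose adjustments may only be made at a clinic visit, including at an unscheduled meeting if needed". SAP 3.2 then states that "subjects are to remain on a fixed dose for an additional 12 weeks", and that those randomized at Visit 7 have been on a fixed dose "for 12 to 16 weeks, without further need for adjustment in medication".

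No denominator specific to dose groups appears in the released text. The general rule in SAP section 6 bases percentages on numbers of subjects. SAP 6.1.8 tabulates subjects per dose level and exposure duration by visit. For Part 3, "summaries will be included of down-titration exposure in the placebo randomized group". It does not add up duration by dose or tie it to the adverse event tables.

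**The concern.** Each event is credited to the dose in use at first onset and expressed as an incidence. An incidence rises with time under observation, and the schedule gives some doses far more time than others. Two doses with identical weekly risk can then show very different percentages, and two doses with different risk can look alike. The planned exposure output is by visit, so a reader could not correct the table from it.

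The safety profile is among the primary objectives (Protocol 3.1, SAP 3.1.1). These are the planned tables that set TEAE incidence against dose, so a false or hidden gradient would matter to anyone who consults them for that purpose.

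**Working it through.** **Time at dose, from the schedule (Protocol 4.1, SAP Table 1).** Visits 2, 3, 4 and 7 fall on Days 8, 22, 36 and 120.

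- Visit 2 to 3: (22 − 8)/7 = 2.0 weeks. Visit 3 to 4: (36 − 22)/7 = 2.0 weeks.
- Visit 4 to 7: (120 − 36)/7 = 12.0 weeks. Visit 2 to 7: (120 − 8)/7 = 16.0 weeks.

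This reproduces the SAP's 12 to 16 weeks. Against a 2-week step, time at risk differs 12/2 = 6-fold to 16/2 = 8-fold. Unscheduled visits can make a step shorter than 2 weeks.

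**Case 1: constant hazard, unmixed doses.** The documents give no TEAE hazard, so the weekly hazard h is an assumption, the same at both doses. Every subject spends 2 weeks at the first dose and 14 at the second.

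First onset at dose 1 = 1 − (1 − h)²; at dose 2 = (1 − h)² × [1 − (1 − h)¹⁴].

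| h per week | Dose 1 | Dose 2 | Ratio |
|---|---|---|---|
| 1% | 2.0% | 12.9% | 6.5 |
| 2% | 4.0% | 23.7% | 6.0 |
| 5% | 9.8% | 46.2% | 4.7 |

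The apparent gap is about 5- to 7-fold with no dose effect. It is smaller for very common events: at a 90% risk over 16 weeks the same calculation gives 2.6.

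**Case 2: constant hazard, mixed doses.** Assume a 20% risk over 16 weeks and c(t) = 1 − 0.8^(t/16), so c(2) = 2.75% and c(14) = 17.7%. If a share s of a dose's takers hold it for 14 weeks and the rest for 2, its incidence is s·c(14) + (1 − s)·c(2).

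| Share of long holders, dose B v dose A | Ratio |
|---|---|
| 100% v 0% | 6.45 |
| 90% v 10% | 3.82 |
| 80% v 20% | 2.56 |
| 70% v 30% | 1.83 |

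**Case 3: hazard falling over time.** Same 20% risk, hazard proportional to 0.5^(t/half-life). The half-life is an assumption.

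| Half-life (weeks) | Decay restarts at each dose, 16 v 2 weeks | Decay runs from start of Part 2, weeks 2–16 v weeks 0–2 |
|---|---|---|
| 1 | 1.30 | 0.35 |
| 2 | 1.89 | 0.99 |
| 4 | 2.97 | 2.11 |
| 8 | 4.33 | 3.49 |

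The last column shows how a real effect can be hidden. With a 1-week half-life, a share 1 − 0.5² = 0.75 of the cumulative hazard falls in weeks 0–2 and about 0.25 in weeks 2–16. A true threefold higher hazard on the later dose would show almost no difference (3 × 0.25 = 0.75).

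**Effect of person-time.** Take Case 1 with h = 2%, counting weeks up to first onset. Dose 1 contributes 1 + 0.98 = 1.98 person-weeks per subject and dose 2 contributes 0.2366/0.02 = 11.83. The rates are 0.0396/1.98 and 0.2366/11.83, both 2.0 per 100 person-weeks, so the spurious gap disappears. Under Case 3 it does not: with a 2-week half-life from the start of Part 2, a cumulative hazard ratio of 0.99 over 7 times the time gives a crude rate ratio of 0.99/7 = 0.14, now favouring the long-held dose. Rates therefore also need a split by time since start.

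**The case against.** A reader might infer that doses held for 12 to 16 weeks will look several times worse than those held for 2. The documents do not support that. Duration belongs to subjects, not doses: a 2-week step for one subject may be the final dose for another, and 16 weeks at one dose means no change after Visit 2. Case 2 shows the dilution. The direction also depends on when events occur, as Case 3 shows. Protocol 4.4.3.1.3 makes tolerable side effects one condition for simply waiting for the next visit. If a dose is left because of an event, that event counts against the short-held dose, which is a bias the other way. These points limit the size and direction that can be claimed. They do not make the table interpretable, since none of this could be read from it.

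A reader might also infer a known distortion in Part 3. The length of the down-titration steps is not visible, subjects kept on active treatment are scheduled for the same 4 weeks (Day 120 to Day 148), and treatment-group totals do not depend on dose at onset. Only the qualitative point stands: a dose at onset during down-titration is transient.

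The tables are descriptive, and no visible objective concerns dose-response in safety. SAP 6.1.8 supplies part of the exposure context. The denominator may be set in table shells that are not part of the released documents or in text that is not shown; the sentence in SAP 6.3.1 that introduces the TEAE summaries is cut short. Even so, the phrase that defines this display is intact, and neither table title mentions person-time. Finally, dose in Part 2 was individually adjusted, so rates by dose remain confounded. That stands, and it calls for a footnote.

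**Conclusion.** The concern holds for Part 2 in this form: the display as written ignores time at dose, which can differ 6- to 8-fold, so crude incidence can mimic or mask a dose effect. With no true dose effect the apparent ratio is about 5 to 7 under a constant hazard and unmixed dose groups, and about 1.8 to 3.8 when 70% to 90% of one dose's takers, against 30% to 10% of the other's, are long holders. It can fall below 1 if events cluster early or drive subjects off a dose. The time ratio follows from the schedule. The incidence ratios rest on assumed hazards, time patterns and mixing shares, none of which the documents give.

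For Part 3 no size can be stated. The primary efficacy result and the randomized comparison of adverse events between arms are unaffected. The change is worth making because safety is a primary objective and the correction is cheap.

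**What to change.** In SAP 6.3.1 and Table 14.3.1.1.14:

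- State the denominator for each dose as the subjects who ever took it in Part 2.
- Show person-weeks at that dose, cumulated over subjects.
- Report first-onset events per 100 person-weeks with a 95% CI, counting time for each term up to its first onset.
- Split these by time since the start of Part 2, for example conversion phase (Visit 2 to 4) and fixed-dose phase (Visit 4 to 7), because crude rates favour long-held doses if the hazard falls over time.
- Footnote that dose was individually adjusted and not randomized, so the table is descriptive.

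In Table 14.3.1.2.14, show the same exposure columns and, in the placebo group, separate the down-titration period from the placebo period, using the exposure data already planned in SAP 6.1.8.

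The cost is SAP wording and a little more programming from dosing data already collected. The tables become wider, and rates for doses with little exposure will be imprecise. Trial conduct does not change.

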## **6.3.2 Clinical Laboratory Tests**

The following tests will be performed at Screening and Visit 7 (end of open-label fixed dose phase or upon early discontinuation):

#### Hematology:

- Red blood cell indices, including RBC count, hemoglobin, and hematocrit
- Total WBC count
- Differential WBC count
- Platelet count

#### Serum chemistry (Full Panel):

- Sodium
- Potassium
- Chloride
- $\cdot$  CO2
- Glucose (random)
- BUN
- Creatinine
- Calcium
- ALT
- AST
- Alkaline phosphatase
- Total bilirubin
- Total protein
- Albumin

## Urinalysis:

- Dipstick for pH, specific gravity
- Microscopic examination of the sediment
- Urine pregnancy test (for women) to be performed at Screening, Visit 4 (Week 6), and Visit 7 (Week 14)

Scheduled laboratory testing will be performed at a central laboratory using sex- and age-appropriate normal ranges. Laboratory tests may also be repeated between scheduled visits at the discretion of the Investigator. In addition, repeat testing should be performed at the end of the study to follow any clinically significant abnormality to resolution/stabilization.

Clinical laboratory testing (hematology, chemistry, and urinalysis) results at each visit (Screening and Visit 7) and its change from Screening (for all continuous clinical laboratory parameters) will be summarized using descriptive statistics (n, mean, 95% confidence interval, standard deviation, minimum, median, and maximum) using Conventional units. Where applicable (e.g., red blood cell indices), results will be presented separately for men and women. For the summary of change statistics, the Baseline mean and standard deviation will be provided for the subset of subjects with available data for the change summary. Summaries will be based on values obtained from the central laboratory only and appropriate visit windows for categorizing results will be established prior to database lock and unblinding.

When more than one laboratory value is available within a given visit window, the latest value will be used for tabulation purposes.

Criteria for possibly significant changes have been established for selected parameters, tabulated below. The numbers and percentage of subjects meeting these criteria will be summarized.

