#### Urinalysis:

- Dipstick for pH, specific gravity
- Microscopic examination of the sediment
- Urine pregnancy test (for women) to be performed at Screening, and Visit 7 (Week 18) and Visit 11

Results for clinical laboratory parameters will be evaluated for clinically significant values according to pre-specified criteria. Laboratory tests may also be repeated between scheduled visits at the discretion of the Investigator. In addition, repeat testing should be performed at the end of the study to follow any clinically significant abnormality to resolution/stabilization.

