# 6.3.3 Vital Signs

Sitting diastolic and systolic blood pressures, resting pulse measurements, respiration, and body temperature (°C) at each visit will be summarized using descriptive statistics (n, mean, 95% confidence interval, standard deviation, median, minimum, and maximum) for measurements during the open-label phase and also by treatment groups during the randomized double-blind withdrawal phase. Similarly, change from Visit 1 at each visit will be summarized using descriptive statistics. For the summary of change statistics, the Baseline mean and standard deviation will be provided for the subset of subjects with available data for the change summary. Appropriate visit windows for categorizing results will be established prior to database lock and unblinding.

For summary purposes, if more than one vital sign measurement is available for an analysis visit, then the latest value of each parameter will be used.

Values considered possibly clinically significant by the Investigator are to be flagged. Criteria for possibly significant changes are presented in the table below. Number and percentages of subjects with values of clinical significance will be summarized for each study Part; in Part 3, summaries will be by treatment group.

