Table 14.3.4.3.1	Chemistry Laboratory Assessments (Safety Population)	
Table 14.3.4.3.2	Chemistry Laboratory Shift Table (Safety Population)  Number and Percentage of Subjects with a Possibly Clinically Significant (PCS)	
Table 14.3.4.3.3	Chemistry Results – Safety Population	
Table 14.3.4.4	Urinalysis Summary (Safety Population)	
Table 14.3.4.5.1	12-Lead Electrocardiogram Parameters in Part 2 (Safety Population)	
Table 14.3.4.5.2	12-Lead Electrocardiogram Parameters in Part 3 (Safety Population)	
Table 14.3.4.5.3	Clinical Interpretation and Categorical Results of 12-Lead Electrocardiogram in Part 2 (Safety Population)	
Table 14.3.4.5.4	Clinical Interpretation and Categorical Results of 12-Lead Electrocardiogram in Part 3 (Safety Population)	

Version 9.0

	C-SSRS Summary of Suicidal Ideation and Suicidal Behavior in Part 1 (Safety
Table 14.3.5.1	Population)
	C-SSRS Summary of Suicidal Ideation and Suicidal Behavior in Part 2 (Safety
Table 14.3.5.2	Population)
	C-SSRS Summary of Suicidal Ideation and Suicidal Behavior in Part 3 (Safety
Table 14.3.5.3	Population)

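### The SAP's latest-value-in-window rule does not exempt the counts of possibly clinically significant (PCS) results; read literally it can understate them, by an amount that cannot be computed and may be zero

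*SAP*

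**What the plan says.** **Laboratory (SAP 6.3.2).** The rule is: "When more than one laboratory value is available within a given visit window, the latest value will be used for tabulation purposes." The following paragraph introduces the PCS thresholds and says: "The numbers and percentage of subjects meeting these criteria will be summarized." In the planned-output list (SAP 9.1), Table 14.3.4.2.3 carries the title "Number and Percentage of Subjects with a Possibly Clinically Significant (PCS) Hematology Results", and Table 14.3.4.3.3 is its chemistry counterpart. On which values enter, the section says: "Summaries will be based on values obtained from the central laboratory only and appropriate visit windows for categorizing results will be established", with the windows to be fixed before lock and unblinding. Extra values are foreseen. Protocol 9.2.5 provides: "Laboratory tests may also be repeated between scheduled visits at the discretion of the Investigator." SAP 6.3.2 adds that "repeat testing should be performed at the end of the study to follow any clinically significant abnormality to resolution/stabilization".

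**Vital signs (SAP 6.3.3).** For summaries, "if more than one vital sign measurement is available for an analysis visit, then the latest value of each parameter will be used". The PCS count is then described per study Part, as the number of subjects having clinically significant values, and by treatment group in Part 3 (Tables 14.3.4.1.3 and 14.3.4.1.4).

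**ECG (SAP 6.3.4).** The section asks for categories of the maximum QTc and of the greatest change from Visit 2. It also averages triplicates, and it repeats the latest-value sentence in nearly the same words as 6.3.2.

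**The concern.** A PCS table exists to show how many subjects had an outlying value. An abnormal result is a common reason to test again, and SAP 6.3.2 itself plans repeats to follow abnormalities until they settle. If the PCS table takes only the last value in a window, it keeps the follow-up result and discards the one that prompted it. A transient abnormality would then be missing from the summary table. Determining the safety profile is one of the primary objectives, so the rule for these tables should be settled before unblinding and not left to the programmer.

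**Working it through.** The plan gives no figure on this point to reproduce. The check covers text, direction, opportunity and scale.

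**1. Is there an exemption?** SAP 6.3.2 including its two threshold tables, Protocol 10.4.5.4 and the table titles in SAP 9.1 contain no any-value or worst-value rule for the PCS counts. Take potassium, where the SAP criterion is 3.0 or below, or 5.8 mEq/L or above. Suppose a central value of at least 5.8 is followed in the same window by one strictly between 3.0 and 5.8. Under the latest-value rule the subject is not counted. Under an any-value rule the subject is.

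**2. Direction.** Let x1, ..., xk be a subject's values in a window in time order, and let I(x) = 1 if x meets the criterion and 0 otherwise.
- Latest-value status = I(xk). Any-value status = max of I(x1), ..., I(xk).
- Hence latest ≤ any for every subject, and so for the count. It also holds for the percentage when windows, baseline and denominator are the same.
- Enumeration for k = 1 to 6: 2 + 4 + 8 + 16 + 32 + 64 = 126 yes/no patterns. Latest exceeds any in 0. It is lower in 0 + 1 + 3 + 7 + 15 + 31 = 57, and equal in 126 − 57 = 69.
- The SAP's systolic PCS rule with a fixed baseline, over 16 × 16 × 16 = 4,096 combinations of baseline and two values: latest PCS without any-value PCS in 0.

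This is a logical certainty and says nothing about frequency. It does not carry over to a difference between arms, which could move either way.

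**3. Can a repeat share a window with the abnormal value?**
- Laboratory: the repeat must come from the central laboratory. Only scheduled testing is stated to be central; discretionary repeats are not.
- Visit 7 is Day 120 ± 1 (Protocol 4.4.4.1) and Visit 11 is Day 148 (SAP Table 1), so the gap is 148 − 120 = 28 days. A ± 1-day window cannot capture the end-of-study repeat. Only a window running to Day 148 would, and Visit 11 has its own as-needed laboratory entry in SAP Table 2. The realistic route is a discretionary repeat close to Visit 7.
- Vital signs: SAP Table 2 marks unscheduled visits at Visits 3 to 7 and none at Visits 8 to 11. In Part 3 the only route is the remark in Protocol 4.1 that subjects may be seen sooner than weekly if required. A subject leaves a per-Part count only if every PCS value in that Part is displaced.

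**4. Scale.** The understatement is N × p × r × s, where p is the share of subjects with a PCS value, r the share of those with a usable repeat in the same window, and s the share of repeats that no longer qualify. The documents give none of p, r or s. All three are assumed below.

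| N | p | r | s | Subjects missed |
|---|---|---|---|---|
| 300 | any | 0 | any | 0 |
| 300 | 5% | 0.5 | 0.5 | 3.75 |
| 300 | 5% | 1 | 0.9 | 13.5 |
| 300 | 10% | 1 | 0.9 | 27 |
| 240 | 5% | 1 | 0.9 | 10.8 |

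The range of 0 to 27 reflects the assumptions and is not an estimate.

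The weight of one displaced subject is 100/N points: 100/300 = 0.33 (enrolled) or 100/240 = 0.42 (minimum randomized) for laboratory tests. For Part 3 vital signs it is 100/120 = 0.83 at an assumed equal split of 240, or 100/160 = 0.63 and 100/80 = 1.25 at an assumed 2:1 split. These denominators are approximate, because the PCS tables use the Safety Population (SAP 5.1) and percentages use subjects with non-missing data (SAP 6).

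**The case against.** The strongest reply is that the latest-value sentence belongs to the by-visit summaries. It follows the paragraph on Screening and Visit 7 statistics and speaks of visit windows. The PCS counts come in a separate paragraph with no visit structure, and the table title refers to subjects with a PCS result. An any-value reading is natural, and table shells not included in these documents may already adopt it. This stands in part: the laboratory text is open, much as the vital-sign text is. But a PCS table is a tabulation, the sentence has no exception, and a programmer who follows it literally would drop the subject.

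A second reply is that neither convention is wrong, since an any-value count keeps spurious results that a repeat corrected. That is fair, and it is why the rule should be stated.

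Four stronger readings are tempting and are not supported:

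- **That the SAP uses a worst-value rule for QTc and so contradicts itself on laboratory tests and vital signs.** SAP 6.3.4 contains the same latest-value sentence. ECG shares the tension and is not a counter-example.
- **That subjects will be lost from the PCS tables.** This needs a central repeat inside a window not yet defined, and the literal reading.
- **That 0.33 to 1.25 points is the size of the bias.** It is one subject's weight.
- **That a safety signal would be hidden or the arm comparison distorted.** Scheduled laboratory data fall at Screening and at Visit 7 or early discontinuation, essentially before randomized treatment. PCS values remain flagged in the listings (SAP 6.3.2; Protocol 10.4.5.3), and an abnormal laboratory finding can be an adverse event (Protocol 9.1.1).

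**Conclusion.** The point holds as a gap in the rules for the PCS tables. SAP 6.3.2 states a latest-value rule and does not exempt the PCS counts; 6.3.3 and 6.3.4 leave the same question open. Compared with an any-value count over the same values, the result is an understatement or zero. The direction rests on keeping windows, baseline and denominator the same. If an any-value count also took in values outside every window, the number of subjects could still only rise, but the percentage could shift with the denominator. No size can be given without the windows and a repeat rate. The consequence is confined to summary tables. Of the laboratory and vital-sign PCS tables, only 14.3.4.1.4 is planned by arm, and no efficacy conclusion is touched. It is worth correcting because the correction is cheap, not because harm has been shown.

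**What to change.** - **SAP 6.3.2 and 6.3.3:** limit the latest-value rule to by-visit descriptive, change and shift tables. State that a subject counts in Tables 14.3.4.2.3, 14.3.4.3.3, 14.3.4.1.3 and 14.3.4.1.4 if any post-baseline value in the given study period, scheduled or unscheduled, meets the criterion. For laboratory tests, keep this to central-laboratory values.
- **Study periods:** report open-label values separately from Part 3 values. The laboratory PCS tables are not titled by Part or arm, so a single pooled count would mix open-label with randomized-period results. Show the as-needed Visit 11 laboratory values by arm and mark them as selectively collected, since Protocol 4.4.4.5 calls for them only to follow adverse events.
- **SAP 6.3.4:** state that the QTc maximum and greatest-change categories use all values and not only the latest, and whether a value there means a triplicate average or a single reading.

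The cost is a short addition to each of the three sections and a small programming change, made before lock and unblinding, when the visit windows are due to be fixed anyway. The downsides are that a spurious value corrected on repeat still counts, that subjects tested more often have more chances to be counted, and that reported PCS rates may be slightly less favourable.
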